8.2. Adverse Event Preferred Term and Body/Organ System Summary Tables

8.2.1. Summaries of Adverse Event Incidence Rates for All Subjects

All AE terms will be coded using MedDRA. TEAEs and TESAEs will be summarized by primary SOC and PT, and also by severity (mild, moderate and severe) and relationship to study drug (related and not related). For a TEAE reported more than once from a patient, the TEAE will be counted only once in the SOC or PT category using the most severe occurrence or closer relationship to the study drug. All AEs will be listed.

The following subsets of TEAEs will be summarized by SOC and PT:

- All TEAEs
- TEAEs related to study drug
- TEAEs leading to early discontinuation of study drug
- TESAEs

A summary of all TEAEs by PT will be provided. AE summaries will be sorted by descending order of SOC in aficamten group and descending order of preferred term within the SOC. TEAE and TESAE summary of $\geq 5\%$ and $\geq 2\%$, respectively will be provided based on incidence rate in either aficamten or placebo group. Summary of TEAEs by maximum severity will display number and percentage of AEs with maximum severity being mild, moderate, or severe within

each SOC and PT. All TEAE summary will also be provided by dose level. Summary of number of events will be provided for all TEAE summary.

8.2.2. Summaries of Adverse Events of Special Interest

The following events are considered adverse events of special interest:

- Incidence of reported major adverse cardiac events (CV death, cardiac arrest, non-fatal stroke, non-fatal myocardial infarction, CV hospitalization)
- Incidence of new onset persistent atrial fibrillation
- Incidence of ventricular arrhythmias requiring treatment

Summary of patients counts and percentage by each event type will be provided by treatment group.

In addition, incidence of appropriate ICD discharges will be summarized for baseline and also post randomization. Incidence of aborted sudden cardiac death will be provided. Number of patients and number of incidences of LVEF <40% and 50% will be provided by treatment group. Number of patients and number of incidences of LVEF <50% and with signs and symptoms of heart failure (concomitant adverse event of heart failure or dyspnea) or experienced $\geq 30\%$ increase in NT-proBNP, relative to results from the most recent previous visit and above the upper limit of normal, at the time of LVEF assessment will be provided by treatment group. Signs and symptoms and NT-proBNP increase referring to AEs with onset date or NT-proBNP assessment date within ± 7 days relative to the date when LVEF <50%.

8.3. Total Duration of Therapy, Final Daily Dose of Study Medication, and Compliance

8.3.1. Summary of IP Exposure and Overall Compliance

Total duration of treatment and total exposure of study drug will be summarized. IP compliance will be derived as:

IP compliance = $100\% * (\text{number of tablets dispensed} - \text{number of tablets returned}) / \text{expected number of tablets administered}$.

Number of tablets dispensed and returned will be collected on the study drug accountability eCRF. For the IP kits not returned, the number of tablets returned will be set to 0 in this derivation, assuming all tablets were taken. Expected number of tablets administered will be derived as the number of daily tablets times the days in an IP dosing period, summed over all dosing periods. Days of dosing interruption will be excluded from the expected number of tablets calculation.

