6.2. Preparation/Handling/Storage/Accountability

The investigator or designee must confirm appropriate temperature conditions have been maintained during transit for all IP received and any discrepancies are reported and resolved before use of the IP.

Only patients randomized in the trial may receive IP and only authorized site staff may supply or administer IP. All IP must be stored in a secure, environmentally controlled, and monitored

(manual or automated) area in accordance with the labeled storage conditions with access limited to the investigator and authorized site staff.

The investigator, institution, or the head of the medical institution (where applicable) is responsible for IP accountability, chain of custody, reconciliation, and record maintenance (ie, receipt, reconciliation, and final disposition records).

Patients should be instructed to take four tablets each day from one row on the blister pack. Further guidance and information regarding IP storage condition, dispensation, packaging, labeling, and accounting procedures are provided in the Pharmacy Manual.

IP should be stored at or below 25°C.

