6.4. Investigational Product Compliance

When patients are dosed at the site, the date and time of the dose administered in the clinic will be recorded in the source documents and recorded in the CRF.

When patients self-administer IP at home, compliance with IP will be assessed at each site visit. Compliance will be assessed by counting returned tablets during the site visits and documented in the source documents and CRF. Deviation(s) from the prescribed dosage regimen should be recorded in the CRF.

For IP accountability, a record of the following should be documented in the CRF at every visit and reconciled with IP and compliance records:

- the date and kits dispensed
- date and tablets returned

IP dosing first and last dates, including dates for dosing interruptions will also be recorded in the CRF.

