5.7.8. Other Study Related Definitions

Actual Dose Group

Patients in the aficamten actual treatment group will be identified as 5 mg, 10 mg, 15 mg, 20mg or discontinuing IP prior to dose adjustment based on the dose assigned at Week 8. If a patient discontinues IP prior to the start of Week 8 (IWRS Week 8 dispensation), then the subject will be

identified as discontinued IP prior to achieve stable dose. The actual dose group may be used in selected displays.

Investigational Product Exposure Period

For subjects dosed with IP:

$[(\text{Last IP administration date} - \text{date of Study Day 1}) + 1]/7$ (in weeks)

Interruptions recorded in the eCRF page will be excluded from the expected dose calculation.

Treatment-emergent Adverse Event

For the purpose of reporting, an investigator-reported event starting on or after first dose of IP and up to and including 28 days after the last dose date of IP will be labeled as a treatment-emergent AE.

Last Titrated Dose

Last titrated dose is defined as the last titrated dose assigned to the patient during the 24 Week treatment period.

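### SAP 8.3.1 counts every tablet in an unreturned kit as taken, which hides missed doses and can put compliance above 100% when a patient stops or interrupts dosing and keeps the kit

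*SAP*

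**What the plan says.** SAP 8.3.1 defines compliance as 100% × (tablets dispensed − tablets returned) / "expected number of tablets administered". The two counts come from the accountability form: "Number of tablets dispensed and returned will be collected on the study drug accountability eCRF". For a kit that does not come back, the rule is: "For the IP kits not returned, the number of tablets returned will be set to 0 in this derivation, assuming all tablets were taken".

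The denominator is "the number of daily tablets times the days in an IP dosing period, summed over all dosing periods", and "Days of dosing interruption will be excluded from the expected number of tablets calculation". SAP 5.7.8 says the same under the exposure period: "Interruptions recorded in the eCRF page will be excluded from the expected dose calculation". That entry runs exposure from Study Day 1 to the last administration date, and Protocol 9.4.9 also ends treatment duration at the last dose. Neither document defines an IP dosing period.

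The SAP gives no cap at 100%, no category for unaccounted kits and no alternative calculation. On the protocol side, section 6.4 states: "Compliance will be assessed by counting returned tablets during the site visits". Section 6.2 fixes the daily count: "Patients should be instructed to take four tablets each day from one row on the blister pack".

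**The concern.** The protocol's method rests on a tablet count, and a kit that never comes back has none. The SAP fills that gap with the most favourable value possible, so unknown intake is reported as full intake.

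The numerator and denominator can also cover different days. An unreturned kit credits all its tablets, including those meant for days after the patient stopped or while dosing was interrupted. Those days are not in the expected count.

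At stake is a reported adherence figure that errs upward wherever kits are unaccounted for, cannot show missed doses in those kits, and can take values that are impossible as a share of prescribed tablets.

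**Working it through.** The documents state no compliance figure, so there is nothing to reproduce. The check applies the SAP 8.3.1 formula to worked patients.

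**Inputs from the documents**
- Four tablets a day (Protocol 6.2).
- Dispensing on Day 1 and at Weeks 2, 4, 6, 8, 12, 16 and 20 (Schedule of Activities). This gives four 14-day and four 28-day intervals: 168 days, 168 × 4 = 672 tablets.
- Expected tablets = 4 × dosing days up to the last dose, less interruption days (SAP 8.3.1, read with SAP 5.7.8).

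**Assumption.** Kit contents are not given. Each kit is taken to hold 4 tablets × interval length (56 or 112), with no overage. A range of 3 or 7 spare days per kit is shown where it matters.

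**Kits returned**
- Stops after 150 days (10 days after Week 20), all doses taken: the last kit is returned with 112 − 40 = 72 tablets. Score (560 + 112 − 72)/600 = 100%, which is correct.
- The same patient with 70% intake throughout scores 70%, also correct.

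**Current kit kept after stopping**
- Stops after 150 days, all doses taken until then: 140 × 4 = 560, plus 112 credited, is 672. Expected is 150 × 4 = 600. Score 672/600 = 112%. For the last interval alone, 112/40 = 280%.
- Stops on day 63, 70% intake: 0.7 × 224 = 156.8, plus 112, is 268.8. Expected is 63 × 4 = 252. Score 106.7%. With 7 spare days in the kept kit, (156.8 + 140)/252 = 117.8%.
- Stops on day 147, 70% intake: (0.7 × 560 + 112)/588 = 504/588 = 85.7%. With 7 spare days, 532/588 = 90.5%. Both are inflated but below 100%.

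**Interruption with the kit kept**
- A 7-day interruption in one 28-day interval: credited 112, expected 21 × 4 = 84, so 133% for that interval. For a completer with otherwise full intake, 672/(161 × 4) = 672/644 = 104.3% overall.

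**Completers who keep kits**
- Half of one 28-day kit taken over 28 days: true 56/112 = 50%, scored 112/112 = 100% for that interval.
- 70% intake, one kit kept: a 28-day kit gives (392 + 112)/672 = 75.0%; a 14-day kit gives (431.2 + 56)/672 = 72.5%. With 7 spare days in the kept kit these become 79.2% and 76.7%.
- No kits returned: 672/672 = 100% whatever was taken. With 3 spare days per kit, (672 + 96)/672 = 114.3%; with 7, (672 + 224)/672 = 133.3%.

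**If the dosing period meant the whole dispensing interval**
- The 150-day patient who keeps the kit scores 672/672 = 100%. The same patient returning the 72 tablets scores 600/672 = 89.3%. The excess over 100% goes, but an unreturned kit still counts as fully taken.

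**The case against.** The strongest reply has four parts.

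*The percentage decides nothing.* Efficacy is analysed in all randomized patients. The secondary estimand turns on completing 24 weeks of treatment, and the PK set on evaluable concentrations and major deviations. This stands. A reader might infer that the rule could distort an efficacy conclusion; the documents give no route for that and do not say how compliance will be used in interpretation.

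*Other evidence on intake is planned.* Treatment duration and total exposure are summarised (SAP 8.3.1, Protocol 9.4.9), as are discontinuations with reasons (SAP 6.1) and pre-dose and post-dose concentrations (SAP 9). Interruptions and regimen deviations go in the CRF (Protocol 6.4). This also stands, so it would be wrong to call the percentage the only planned evidence on adherence.

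*The large values rest on unseen inputs.* Protocol 6.2 leaves packaging and accounting to the Pharmacy Manual, and the dosing period is undefined. This stands as a limit on size. The 280% is also a one-interval figure, whereas the SAP sums over all periods, so 112% is the relevant result for that patient. A kit holding less than its interval can score below 100%: a 28-day supply over 35 dosing days gives 28/35 = 80%.

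*Dropping unreturned kits does not recover what was taken from them.* This is true. A completer with full intake except half of one kept 28-day kit has a true value of (560 + 56)/672 = 91.7%. The present rule gives 100%, and so does the counted-kits rule (560/560). The difference is that the second shows beside the score that a kit is unaccounted for.

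**Conclusion.** The point holds as a one-directional bias in a descriptive summary and should be corrected. Wherever a kit is unreturned, missed doses in it are invisible. A score above 100% in the no-overage examples needs both a stop or interruption and an unreturned kit: 112% over the trial for the 150-day case, 106.7% for the day-63 case at 70% intake, and 104.3% for a completer with one 7-day interruption. These rest on kits sized exactly to their intervals and on dosing days ending at the last dose. SAP 5.7.8 supports the latter but does not settle it.

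Three stronger readings are not supported:
- **Early stopping alone inflates the score.** It does not; returned tablets are subtracted and the true ratio results.
- **Any kept kit brings the score to 100%.** A completer at 70% intake who keeps one kit scores 72.5% to 75.0% without overage.
- **The bias favours one arm.** The documents give no rate of unreturned kits. Protocol 2.3.1 reports LVEF below 50% in 2 of 41 active patients and in none on placebo, but interruption is tied to LVEF below 40%, and no such value was reported. The effect on arm-level means is unknown.

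**What to change.** Amend SAP 8.3.1 as follows:
1. Define the IP dosing period as the days from first to last dose within each dispensing interval, less recorded interruption days.
2. Compute compliance only over kits with a tablet count. Remove an unreturned kit and its days from both numerator and denominator. The day-63 patient at 70% intake then scores 156.8/224 = 70.0%.
3. Report by arm the number of kits unaccounted for and the number of patients with at least one.
4. If the all-taken rule is kept, show it only as a labelled upper bound, with credited tablets capped at the expected number for that period.

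The cost is a short SAP edit and minor programming. No new data are needed, because Protocol 6.4 already records kits dispensed and tablets returned at every visit, and no efficacy or safety analysis changes. The drawbacks are that some periods, and patients who return nothing, have no score; that the percentage describes counted kits only and says nothing about the missing ones; and that mean compliance may look slightly less favourable.

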8.3.2. Summary of Dose Titration

IWRS-guided dose titration will be summarized showing the number and percentage of patients at each dose level by visit. Number and percentage of patients by last titrated dose will be provided.

8.4. Concomitant and Other Medications

Concomitant medications reported on the eCRF will be summarized. Medications with a start date that is 28 days after the last dose of the study drug will be excluded from the summary. The WHO Drug Dictionary will be used to classify medications by therapeutic class (ATC Class 3) and preferred name. If ATC Class 3 is not available, ATC Class 2 will be used in the summary. Coding will be performed using WHO Drug Dictionary.

8.5. Routine Laboratory Data

Clinical chemistry, hematology and urinalysis laboratory measurements and value changes from baseline at each laboratory blood sample collection time point will be summarized. Values below or above the quantifiable limits will be treated as equal to the limits in the summary. The count and percentage of patients who had normal or missing laboratory values at baseline and abnormal laboratory values post baseline will be presented. The lower limit of normal (LLN) and upper limit of normal (ULN) provided by the laboratories will be used as the criteria to determine abnormality. For each parameter, the denominator of the percentage will include patients with normal or missing assessments at baseline, and with at least one assessment post baseline. The numerator of the percentage will include patients who had at least one abnormal assessment post baseline among the patients that were counted in the denominator. Assessment collected at unscheduled visits, or the Follow-up Visit will be included in the summary.

Shift of clinical laboratory results from baseline severity to the maximum post baseline severity will be presented for selected laboratory parameters.

Liver function test results will be summarized as count and percentage of patients with normal baseline and abnormal post-baseline values in Alanine Aminotransferase (ALT), Aspartate Aminotransferase (AST), Alkaline Phosphatase (ALP) and bilirubin, with the following categories:

- ALT > 3xULN, > 5xULN, > 8xULN
- AST > 3xULN, > 5xULN, > 8xULN
- ALT and/or AST > 3xULN, > 5xULN, > 8xULN
- ALT and/or AST > 3xULN and total bilirubin > 2xULN and ALP < 2xULN
- ALT and/or AST > 3xULN and total bilirubin > 2xULN
- Bilirubin (total, indirect or direct) > 2xULN, >3xULN
- ALT or AST > 3 x ULN with symptoms including nausea, vomiting, anorexia, abdominal pain, fatigue, rash, dark-colored urine, light-colored bowel movements, jaundice, or fever

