215. Hepatic impairment defined by a total bilirubin (TBL) $\geq 1.5 \times$ the upper limit of normal (ULN), or alanine aminotransferase (ALT) or aspartate aminotransferase (AST) $\geq 3 \times$ ULN at screening. Patients with documented Gilbert syndrome and TBL $\geq 1.5 \times$ ULN due to unconjugated hyperbilirubinemia, without other hepatic impairment, are permitted.
216. Recipient of a major organ transplant (eg, heart, lung, liver, bone marrow, renal) or anticipated transplantation within 12 months from randomization.
217. History or evidence of any other clinically significant disorder, malignancy, active infection, other condition, or disease that, in the opinion of the investigator or the Medical Monitor, would pose a risk to patient safety or interfere with the trial evaluation, procedures, or completion.

218. Estimated glomerular filtration rate (eGFR) <30 mL/min/1.73 m² (by the modified Modification of Diet in Renal Disease equation) at screening.
219. Currently participating in another investigational device or drug trial or received an investigational device or drug <1 month (or 5 half-lives for drugs, whichever is longer) prior to screening. Other investigational procedures while participating in this trial are not permitted.

Note: At the EOS visit for CY 6031, screening assessments for entry into an open-label extension study of aficamten are permitted.
220. Has received prior treatment with CK-3773274 or mavacamten.
221. Any known hypersensitivity to excipients in study drug tablets

Exclusion Criteria for CMR sub-study

222. Inability to tolerate CMR.
223. Has an ICD.
224. Has a cardiac pacemaker.
225. Does not consent to participate in CMR sub-study

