8.3.5. Laboratory Assessments

See Appendix 2 ([Section 10.2](#)) for the list of clinical laboratory tests to be performed and see the SoA ([Section 1.3](#)) for the timing and frequency.

Repeat or unscheduled samples may be taken for safety reasons or for technical issues with the samples.

The investigator must review the laboratory report, document this review, and record any clinically significant changes occurring during the trial in the AE section of the CRF. Clinically significant abnormal laboratory findings are those which are not associated with the underlying

disease, unless judged by the investigator to be more severe than expected for the patient's condition.

All protocol-required laboratory assessments, as defined in Appendix 2 ([Section 10.2](#)), must be conducted in accordance with the laboratory manual and the SoA ([Section 1.3](#)).

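### SAP 8.5 counts liver threshold crossings only in patients with normal baseline, although eligibility admits raised ALT, AST and bilirubin, and it sets no baseline condition for rows that combine analytes

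*SAP*

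**What the plan says.** SAP 8.5 introduces its list of liver categories with this sentence: "Liver function test results will be summarized as count and percentage of patients with normal baseline and abnormal post-baseline values". The analytes named are ALT, AST, ALP and bilirubin. The rows below include single-analyte thresholds, rows for either transaminase, combined rows such as "ALT and/or AST > 3xULN and total bilirubin > 2xULN", a row for transaminase elevation with symptoms, and "Bilirubin (total, indirect or direct) > 2xULN, >3xULN".

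The general abnormality table in the same section has its own rule: "For each parameter, the denominator of the percentage will include patients with normal or missing assessments at baseline". That rule works one parameter at a time and keeps missing baselines. The liver sentence says neither. A further display is promised: "Shift of clinical laboratory results from baseline severity to the maximum post baseline severity will be presented for selected laboratory parameters". The parameters are not named.

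Criterion 215 in Protocol 5.2 excludes ALT or AST only from 3xULN and total bilirubin only from 1.5xULN. Patients with documented Gilbert syndrome whose bilirubin reaches that limit "due to unconjugated hyperbilirubinemia, without other hepatic impairment, are permitted". Eligibility is judged at screening, whereas SAP 5.6 takes baseline as the last value before first dose. The Schedule of Activities repeats the laboratory panel on Day 1.

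**The concern.** The population of the table is narrower than the population the trial enrols. An eligible patient who starts with a mildly raised transaminase can reach any multiple of ULN on treatment without entering the matching row. The combined rows, which are the ones used to screen for drug-induced liver injury, do not say whether one, some or all of their analytes must be normal at baseline. Two programmers could produce different counts from the same data.

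At stake is the completeness of the by-arm liver counts in the study report. No efficacy result, hypothesis test or dosing decision depends on this table.

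**Working it through.** The plan gives no figure to reproduce, so the check is to pass eligible baseline profiles through the rows.

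**Rows in SAP 8.5.** ALT 3 + AST 3 + either transaminase 3 + transaminase with bilirubin and an ALP condition 1 + transaminase with bilirubin 1 + bilirubin 2 + transaminase with symptoms 1 = 14.

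**Outcome by profile**, reading normal baseline analyte by analyte:

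| Baseline profile (all eligible) | Cannot count | Undefined | Unaffected |
|---|---|---|---|
| ALT only above ULN | 3 (ALT) | 3 either + 2 combined + 1 symptoms = 6 | 3 AST + 2 bilirubin = 5 |
| AST only above ULN | 3 (AST) | 6 | 3 ALT + 2 bilirubin = 5 |
| ALT and AST both above ULN | 3 + 3 + 3 + 1 = 10 | 2 combined | 2 bilirubin |
| Gilbert: total and indirect bilirubin raised, direct normal | 0 | 2 bilirubin + 2 combined = 4 | 3 + 3 + 3 + 1 = 10 |

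Each line sums to 14. The reading matters:

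- If total bilirubin alone sets baseline status, the Gilbert patient also loses the 2 bilirubin rows (2 lost, 2 undefined, 10 unaffected).
- If all four tests must be normal, every profile above leaves all 14 rows.
- Under every reading, a raised ALT removes the patient from the ALT rows, and a raised AST from the AST rows.

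**Illustration.** A patient going from ALT 1.2xULN to 9xULN has a 9/1.2 = 7.5-fold rise, passes all three thresholds and appears in none of the ALT rows. From 2xULN, crossing 3x, 5x and 8xULN takes rises of 3/2 = 1.5, 5/2 = 2.5 and 8/2 = 4-fold.

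**Size.** The documents do not say how many patients start above ULN. Assuming 2% to 20% for ALT: 0.02 x 270 = 5.4 and 0.20 x 270 = 54. These are patients who cannot count in the ALT rows, not threshold crossings missed.

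**Baseline conditions elsewhere.** The documents are mixed. In Protocol Appendix 5, the interruption schedule lists any baseline AST or ALT (for patients without underlying liver disease who do not meet the discontinuation criteria), while the permanent-discontinuation table lists only values below ULN. The vital-sign and QTcF threshold displays (SAP 8.6 and 8.7) carry no baseline restriction; the ECG morphology display counts only new findings.

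**The case against.** The strongest reply is that a normal-baseline table is a legitimate view of treatment-emergent change and that these patients are visible elsewhere. Much of that stands.

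- SAP 5.1 puts minimum and maximum in the descriptive summaries, so a high value at a summarised visit shows as the maximum. This is partial cover: the panel is scheduled after Day 1 only at Weeks 12, 24 and 28 and at early discontinuation, and under SAP 5.7.7 an unscheduled peak gives way to a scheduled value in the same window. A maximum also gives no count.
- Investigators must "record any clinically significant changes occurring during the trial in the AE section of the CRF" (Protocol 8.3.5), and Protocol 8.4.1.1 includes laboratory abnormalities that lead to interruption of investigational product. The 9xULN example lies above the 8xULN interruption threshold in Appendix 5, so it would probably be recorded as an AE. Other isolated rises depend on the investigator's judgment of clinical significance, and AEs are tabulated by system organ class and preferred term, not by multiple of ULN.
- Transaminase elevation together with bilirubin or INR elevation must be reported as an SAE under Appendix 5. The most serious cases therefore do not depend on this table.
- Missing baselines should be rare, since the panel is scheduled at both screening and Day 1 and criterion 215 needs the screening values.
- The display specifications are a separate document (SAP 11.3) and may already contain an all-baseline table.

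A reader might infer that anyone with any raised liver test drops out of the ALT and AST rows. That does not follow: read per analyte, a patient with only bilirubin raised stays in them, and a patient with only ALT raised stays in the AST rows. A reader might also infer that liver injury would be hidden, or that the active arm is favoured. The AE and SAE routes argue against the first. The second has no support, because the restriction applies to both arms and has no built-in direction.

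**Conclusion.** The point holds as an incomplete count. On the SAP's own words, patients with raised baseline ALT are outside the three ALT rows, and likewise for AST. The baseline condition is undefined for the rows that combine analytes and for bilirubin when only some fractions are raised. No display named in the SAP supplies a by-arm threshold count for all baselines: visit summaries do not count, the general abnormality table also drops raised baselines, and the shift table names no parameters.

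The number of missed crossings is unknown and may be small, possibly zero. The range of 5 to 54 patients rests wholly on the assumed 2% to 20%; it must not be read as missed events. Liver thresholds are not among the listed safety endpoints or adverse events of special interest, and the analysis is descriptive. Severity is low. The conclusion also assumes that the separate display specifications do not already close the gap.

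**What to change.** In SAP 8.5:

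1. Tabulate each liver category by arm, using the worst post-baseline value, in all safety-set patients with at least one post-baseline value.
2. Split each count by baseline status: normal, above ULN, and any missing shown separately.
3. State the baseline rule for multi-analyte rows. One workable convention classes baseline as above ULN if any analyte in the row was above ULN; others are acceptable if stated.
4. Name the bilirubin fraction that sets baseline status.
5. List every patient who meets the combined ALT/AST and bilirubin criteria.

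If the display specifications already contain such a table, SAP 8.5 need only refer to it. If the SAP is not reopened, SAP 5.4 allows a change to the planned analysis to be documented in the study report.

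The cost is some wording and one table from data already collected. The drawback is that patients who start above ULN, including Gilbert patients, enter the overall counts; the split makes this visible and keeps the normal-baseline view intact. The change concerns tabulation only and leaves the protocol's clinical liver rules as they are.
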